PROTOCOL: Neurobiological and Psychological Benefits of Exercise in

Chronic Pain & PTSD

NCT#- 03283163

(1). Rationale:

(a). Statement of the Problem.

The wars in Iraq and Afghanistan are creating a new generation of Veterans, including an increasing number of women Veterans, who present with comorbid PTSD and chronic pain conditions from recent deployment-related physical injuries and exposure to psychological trauma. Health behavior change has become increasingly important in treating these conditions and proactively preventing long-term negative health sequelae, in order to benefit these Veterans directly and reduce the growing challenges to our healthcare system. The proposed CDA-2 program of research will use an innovative translational research approach to study whether a chronic progressive -based exercise program will reduce chronic pain in patients with PTSD and to elucidate and modify potential PTSD-related deficiencies in neurobiological and psychological responses to exercise to optimize the physical and psychological benefits of exercise for these individuals.

(b). Hypotheses or Key Questions.

The overall aims and hypotheses of the current protocol are:

Aim 1: Assess the degree of clinical change in chronic pain and PTSD symptoms between the screening session, baseline and endpoint assessment time-points across a 12-week progressive exercise training program.

Hypothesis 1: As compared to the screening evaluation and baseline exercise assessment, as a result of the progressive exercise training regimen, participants will experience clinically significant reductions in pain related symptoms as well as improvements in symptoms of PTSD by the endpoint exercise assessment (between week 13-15).

Aim 2: Compare the impact of the exercise training program on plasma levels of the anti-stress neuromodulator, allopregnanolone plus pregnanolone (ALLO +PA), among trauma-exposed participants with comorbid chronic pain and vary degree of PTSD symptom severity (CP/PTSD).

Hypothesis2a: At the baseline exercise assessment, ALLO +PA will be lower and increase less in response to the maximum load exercise than during the endpoint exercise assessment (week 13).

Aim 3: Determine whether maximum load exercise-induced increases in plasma ALLO+PA correlate with changes in pain symptoms as measured by the cold pressor test and self-reported pain ratings.

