Design Overview: The proposed research will assess the effects of aerobic and anaerobic exercise on ALLO+PA levels and changes in pain sensitivity among male and female Veterans with trauma exposure, chronic musculoskeletal pain and varying degrees of PTSD symptom severity. A total sample size of 30 participants (15 male & 15 female), aged 18-60 years, will be studied. To control for menstrual cycle effects, the women will be tested during the early follicular phase of the menstrual cycle when estrogen levels are low, and levels of progesterone (the steroid precursor for ALLO+PA) are stable and comparable to those in men. However, we will not be excluding women who are perimenopausal/menopausal. These patients will be scheduled during the same timeline as the male participants.

Recruitment methods Fliers will be posted within the VA and advertisements in the community.

Participant Characteristics: Participants will be receiving care in the VA Boston Healthcare System (VABHS) or recruited from the community. Inclusion criteria for the proposed study will permit the recruitment of women as well as men from all ethnic and racial backgrounds who are at least 18 years of age, and able to speak and understand English. The patient population at the VABHS is 65% Caucasian, 15% African American, 10% Latino, and 10% Asian. We intend to sample a similar demographic population as that served by the VABHS and will oversample for minorities to ensure that enough are seen.

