Inclusion Criteria: Only participants in whom a physical examination, medical history, EKG, and baseline laboratory studies including urine toxicology screens indicate that the symptoms limited cardiopulmonary exercise stress ((MAX-EX) testing will be safe will be included in this study. Also, participants will be required to start at a relatively sedentary level, defined as performing less than 30 minutes/day (150 minutes per week) of moderate physical activity on ≥ 5 days per week.⁸² Participants must be free of medications and other substances (e.g., illicit drugs and alcohol) with effects that could hinder data interpretation for 2-6 weeks depending on the medication and frequency of use (which must be cleared by the PI's primary mentor). However, psychotropic medications are allowed as long as the participant has been stable on them for two months. Those who are using tobacco will still be included in the study and will not be required to lower or stop their dosage/intake. If on pain medications with short half-lives,

participants must be off of them for 5 half-lives before testing, generally about 24 hours. Any participant with an ICD-9 or ICD-10 chronic pain diagnosis with a musculoskeletal etiology, as confirmed by the rehab medicine doctor or other qualified pain psychology staff, will be allowed for inclusion in the study. Any participant with a confirmed psychiatric diagnosis of PTSD, including those who are sub-threshold PTSD, or with trauma exposure without a diagnosis of PTSD, other psychiatric conditions, or chronic pain will be included in the study. Individuals in the PTSD group must meet for current chronic PTSD (≥ 3 months) or sub-threshold PTSD as assessed by the CAPS -5, 1-Month Diagnostic Version. Sub-threshold PTSD is determined using the CAPS-5. If a patient endorses 2 or 3 B-E criteria or all B-E criteria without functional impairment – with functional impairment defined as having clinically significant symptoms that interfere with daily activities. Subjects with chronic pain For individuals eligible for the polytrauma group (chronic pain, PTSD and mild and moderate TBI), any participant with a mild or moderate TBI (six months or longer post injury), as determined by the BAT-L will be included.

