Measures of each of the key domains of the chronic pain experience (i.e., pain, affective distress, and disability), PTSD symptoms, TBI symptoms, exercise behavior, and motivation will be administered. Each measure has substantial evidence supporting its reliability and validity, as well as evidence of sensitivity to treatment effects. The current assessment battery was adapted from a previously funded study of pain and PTSD. Please refer to Table2, at the end of the protocol, for the timeline of administration of the following assessments:

Screening Interview Measures:

To be administered at: Screening Evaluation

Structured Clinical Interview for DSM-5 (SCID)⁴³ The SCID is a clinician-administered interview used to assess DSM-5 diagnoses. The instrument has been successfully used across diverse clinical populations and is currently in widespread use in both clinical and research capacities where it is generally considered a gold-standard.

Plan for use of SCID assessment data: We plan to use all of the modules of the SCID in order to better assess for eligibility based on the psychiatric inclusion/exclusion criteria. However, since this assessment is being used purely as a screening tool to determine study eligibility, the information will not be used analytically except for that pertaining to depression and PTSD. We will track all participants Axis I diagnoses in order to provide the necessary descriptive data for publications.

Clinician-Administered PTSD Scale-5⁴⁴⁻⁴ **(CAPS-5)**⁴⁶

To be administered at: Screening Evaluation & Endpoint 13 week exercise test sessions

This 30-item structured interview is designed to assess both the 17 symptoms of PTSD and the 8 hypothesized associated features. The scale yields a dichotomous diagnosis of PTSD, and also provides a continuous score of frequency and severity for each symptom. In addition, a behaviorally anchored probe question is provided for each symptom to increase the reliability of administration. The CAPS-5 is currently in the process of being validated however its previous version demonstrated excellent sensitivity (.81) and specificity (.95).⁴⁵

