Aim 1 : Hypothesis one will be evaluated by conditional LGMs. The Intercept of the LGM will be centered on the self report data from the baseline CPX assessment (i.e., first Slope loading will be fixed to 0.0). The intermittent time point (midpoint self-report session) will be freely estimated and the final time point (i.e the self-report data from the 13 week MAX-EX test session) will have a corresponding Slope factor loading fixed to 1.0. Accordingly, the mean and variance of the Slope factor will convey the fixed (average) and random effects (individual differences) of change for the time interval of interest. The two study groups will be dummy coded (using chronic pain/PTSD as the reference condition in the initial models) and included as predictors in the LGM to account for individual differences in symptom reduction (i.e. pain intensity, pain tolerance and threshold, depression and PTSD symptoms) due to treatment assignment. The Intercept will be regressed onto the treatment covariates to examine any pre-exercise training differences among treatment conditions. Moreover, individual differences in pre-treatment functioning will be held constant by regressing the Slope onto the Intercept. Hypotheses 1 will be supported in part by the statistical significance of the study group (dummy code) > Slope paths. In fact, these paths reflect study group x Time interaction effects. The nature of these interaction effects in the LGMs will be characterized using the procedures described by Curran, Bauer, and Willoughby.⁷⁸ All outcome measures will be analyzed in this fashion.

Aims 2 & 3: At both exercise assessment time-points, change scores will be computed ALLO+PA and these will be correlated with pain tolerance and pain threshold scores using Pearson or Spearman correlations, as appropriate. For exploratory purposes, ALLO+PA will be used as predictor variables in a regression equation to predict pain outcome (tolerance, threshold and intensity).

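### The Aim 1 growth model codes a recruited range of PTSD severity as two inconsistently defined groups, and ties support for Hypothesis 1 partly to that code

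*Combined protocol and SAP*

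**What the plan says.** The Design Overview in section (4)(b) describes the sample as "male and female Veterans with trauma exposure, chronic musculoskeletal pain and varying degrees of PTSD symptom severity". Aim 2 in section (1)(b) refers to "trauma-exposed participants with comorbid chronic pain and vary degree of PTSD symptom severity (CP/PTSD", and the Summary at the end of the Background repeats the idea. The CAPS-5, given at screening and endpoint, "provides a continuous score of frequency and severity for each symptom". The PCL-5 supplies a second continuous measure.

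For Aim 1, the Data Analyses section specifies a latent growth model over three time points, with Slope loadings fixed at 0, free, and fixed at 1. Group enters as follows: "The two study groups will be dummy coded (using chronic pain/PTSD as the reference condition in the initial models". The decision rule is "Hypotheses 1 will be supported in part by the statistical significance of the study group (dummy code) > Slope paths". Hypothesis 1 itself states that "participants will experience clinically significant reductions in pain related symptoms as well as improvements in symptoms of PTSD".

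The text varies on what the groups are:

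- **Inclusion Criteria, section (4)(b):** "Individuals in the PTSD group must meet for current chronic PTSD (≥ 3 months) or sub-threshold PTSD as assessed by the CAPS -5". The same paragraph admits trauma-exposed people without PTSD and, on one reading, without chronic pain. It also mentions a polytrauma group.
- **Chronic Exercise Rehabilitation Training Program:** trauma-exposed controls are trained alongside patients.
- **Data Analyses, opening lines:** two treatment conditions.
- **Human Studies Section, on subject characteristics and on sources of materials:** four study groups.
- **Recruitment and Informed Consent:** the invitation also covers trauma-exposed people who do not meet the pain and/or PTSD criteria.

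The analysis paragraph for Aims 2 and 3 correlates ALLO+PA change scores with cold pressor tolerance and threshold. It has no PTSD severity term. The Exploratory Aim lists PTSD severity among the measures to be intercorrelated.

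**The concern.** There are two separate problems.

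First, a path from group to Slope shows whether two groups change by different amounts. It can be zero when everyone improves, and non-zero when the average change is zero. It therefore does not test Hypothesis 1.

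Second, the dummy is the only between-person variable, apart from each outcome's own Intercept, that the model offers to explain differences in Slope. Full and sub-threshold PTSD share one group, so a sub-threshold case is coded the same as a severe one. For pain and depression outcomes, no planned model asks whether the continuous severity score changes the slope.

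The study is a pilot meant to supply effect sizes for a later trial. With 25 to 30 people, the answer on severity would depend on a group boundary that is not clearly written down, and it may discard information already collected.

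**Working it through.** **1. The plan's own figures.** The Power and Sample Size section gives N = 25 for 90% power at an effect size of .35 (two-sided 5%), and power .94 at 30. The two figures agree with each other: (1.960 + 1.282) × √(30/25) = 3.551, and 3.551 − 1.960 = 1.591, which gives power .944. The type of effect size is not stated. Read as Cohen's d in a paired test, .35 would need 88 people. Read as Cohen's f over three repeated measures with an assumed correlation of .3, it gives N = 26, power .89 at 25 and .94 at 30. None of these figures concerns grouping, so the plan has no stated loss to reproduce.

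**2. Information kept by a two-group code.** For a linear severity effect, the relative efficiency of the code against the score is corr(code, severity)². For a normal score cut at proportion p this equals φ(z_p)² / [p(1 − p)].

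- Median: .3989² / .25 = .637, a loss of 36%. Then 25 people act like 15.9 and 30 act like 19.1.
- 67/33: .593, a loss of 41%.
- 80/20: .490, a loss of 51%.
- 90/10: .342, a loss of 66%.

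For other shapes:

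- Uniform score cut at the median: 3 × .25 = .75, a loss of 25%.
- Exponential (right-skewed) score cut at the median: (ln 2)² = .480, a loss of 52%.
- Two equal clusters s within-cluster SDs apart, coded by cluster: (s²/4) / (1 + s²/4). The loss is 50% at s = 2, 31% at s = 3 and 20% at s = 4.

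These cases span about 20% to 66%. The span is not a bound: an exponential score cut at its 20th percentile keeps only .199. The documents give no group sizes (only 15 men and 15 women) and no severity distribution, so every case is an assumption.

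**3. What this means for power.** By Fisher's z, power ≈ Φ(atanh(r)·√(n − 3) − 1.96). With a median split, r is multiplied by √.637 = .798.

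- n = 25, r = .5, score: .5493 × 4.690 − 1.96 = .616, power .73.
- n = 25, r = .5, split (r = .399): .4224 × 4.690 − 1.96 = .021, power .51.
- With the small-sample term r/[2(n − 1)] added to atanh(r), these become .75 and .52.
- n = 30, r = .5: .81 against .59.
- n = 25, r = .3: .31 against .21.
- n = 25, r = .6: .90 against .69.

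The correlations are assumed. The calculation treats change as a simple observed score, not as a latent Slope conditional on the Intercept.

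**4. Whether the dummy is a cut on severity.** If everyone has chronic pain, as Aim 2 and the Design Overview say, the second group can only be people with chronic pain and less or no PTSD, and no boundary is given for the model. If pain-free trauma-exposed controls are enrolled, the dummy carries pain status as well as PTSD. Steps 2 and 3 apply to the first reading only.

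**The case against.** The strongest reply is that the dummy is a diagnostic contrast, not a split of a score. Nowhere does the plan say that participants will be divided at a CAPS-5 value, and several sections point to a comparison with trauma-exposed controls. On that reading, replacing the dummy with CAPS-5 changes the question instead of recovering lost information. This stands, and it is why the loss is conditional and why pain status needs its own term.

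A reader might infer that the plan loses about a third of its information on severity. The documents do not support that as a fact: the figure needs a normal score and a median cut, and neither is stated.

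A reader might also infer that PTSD severity is ignored outside the dummy. It is not. The Exploratory Aim correlates it with ALLO+PA and pain measures, and for PTSD outcomes the regression of Slope on Intercept already brings baseline severity in as a continuous variable. What is missing is severity as a predictor of Slope for pain, cold pressor and depression outcomes, and as a predictor of change in ALLO+PA response.

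Finally, no hypothesis names severity as a moderator of change, and Aim 2's wording may only describe the population. That is fair. However, the plan raises the moderator question itself by making the group-to-Slope path part of the evidence for Hypothesis 1. It is also true that at r = .3 neither coding has useful power.

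**Conclusion.** The mismatch is real. One population with varying severity is described, a two-group code with an unsettled second group is analysed, and the path from that code is offered as partial support for a hypothesis it does not test.

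The size of the information loss is conditional. If the groups are in effect a cut on severity and the effect is linear, the loss is 36% for a normal score cut at its median and about 20% to 66% over the other cases listed. At n = 25 and r = .5, that median cut takes power from about 73–75% to 51–52%. If the groups are instead patients and pain-free controls, these figures do not apply, and the problem is that the dummy mixes PTSD with pain status. Neither reading supports leaving the text as it is. The change should be made, but it does not invalidate the data collection.

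**What to change.** Amend the Data Analyses section as follows.

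1. **Groups.** State how many groups exist and who belongs to each, and make the eligibility, consent and analysis sections agree.
2. **Hypothesis 1.** Judge it by the mean of the Slope factor, estimated without predictors or as the model-implied mean. Once Slope is regressed on Intercept and group, its own constant refers to the reference group at an Intercept of zero.
3. **Moderator analysis.** Replace the dummy with the centred CAPS-5 total as predictor of Intercept and Slope for pain, cold pressor and depression outcomes. Use the last CAPS-5 before training, since the plan repeats it when a month or more passes after screening. If any participants without chronic pain are enrolled, add a separate term for pain status.
4. **Aim 2.** Regress the baseline-to-endpoint change in ALLO+PA response on the same score, in addition to the exploratory correlations.
5. **PTSD outcomes.** Report any severity term as descriptive only. Baseline severity already enters through the Intercept, and the predictor and outcome share regression to the mean.
6. **Diagnosis.** Keep it for describing the sample.

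The cost is analysis wording; no new data are needed. The downside is the assumption of a roughly linear severity effect, which a plot of individual change against CAPS-5 can check.

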Hypothesis 3a: At the baseline exercise assessment, diminished acute (maximum load) exercise-induced increases in ALLO+PA will be

associated with lesser acute exercise-induced decreases in pain sensitivity and lesser increases in tolerance as measured by the cold pressor test.

Hypothesis 3b: At the endpoint exercise assessment at the end of the progressive, intense exercise training regimen, MAX-EX-induced increases in plasma ALLO+PA will correlate with increases in pain tolerance/decreases in pain sensitivity when compared to baseline pre-training responses.

Exploratory Aim 1: Assess the role of exercise motivation and self-efficacy in relation ALLO+PA responses to exercise at the screening, baseline and endpoint exercise assessments.

Hypothesis: Participants with higher acute exercise-induced increases in ALLO+PA will show significantly higher levels of intrinsic motivation and self-efficacy for exercise, as well as lower levels of pain sensitivity (tolerance and threshold), pain-related symptoms and PTSD severity. Increases in intrinsic motivation will parallel increases in acute exercise-induced increases in ALLO +PA as the participant's progress through the 12-week chronic exercise training regimen.

(c) Specific Objectives.

Our main objective is to first determine if there are clinical, antinociceptive and anti-stress benefits of exercise for the trauma-exposed, chronic pain/PTSD population. Our second objective is to begin to delineate the interrelated pathophysiology of chronic pain and PTSD through our investigation of neurobiological factors such as ALLO+PA. These findings would ultimately inform development of more effective therapeutic interventions for these commonly comorbid conditions. For example, data from this pilot work will be used to compute effect sizes in support of a future clinical trial incorporating individually prescribed exercise regimens and a motivationally based exercise behavior change intervention aimed at reducing pain and PTSD symptoms in our Veterans. Specifically, this CDA-2 will allow the PI to develop a more effective, motivationally based, exercise behavior change protocol that fosters long-term exercise compliance in patients with chronic pain/PTSD which will be used as an adjunct to cognitive interventions for these disorders to be further developed and studied via a larger VA, NIH, or DOD-funded grant for which the PI will apply in years 4-5 of the CDA2.

2. Background and Significance

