These findings have further helped to develop the exploratory hypothesis of the current proposal in investigating whether such motivational states (integrated regulation and self-efficacy) is associated with NPY and ALLO levels. Specifically, an improvement in NPY and ALLO levels through chronic exercise training could also help to improve the motivational states necessary to adhere to long term exercise training.

Pilot data:

Pilot Project: Specific outcomes related to preliminary study hypotheses (as previously proposed):

Analyses were performed using SPSS bivariate correlation, regression and frequencies for evaluation of assumptions. A square root transformation was used to reduce skewness and improve the normality of the data when needed (e.g. for the variable "change in NPY from baseline to five minutes post-exercise").

Hypothesis: At baseline, NPY and ALLO levels will be lower in the Pain/PTSD group compared to the TC group.

GABAergic neuroactive steroid levels measured at baseline just prior to the initiation of maximum load exercise, at peak exhaustion (~VO₂ max), and 30 minutes after exercise. Steroids were separated by high pressure liquid chromatography (HPLC) and then measured by gas chromatography-mass spectrometry (GC-MS). Consistent with previous work in rodents (Purdy et al., 1996),

allopregnanolone/pregnanolone appeared not to peak until about an hour after the initiation of exercise stress. Examination of the mean change in ALLO (normalized by BMI) from baseline to post thirty minutes of exercise by sex indicated that for both women and men, the TC's had a greater total mean sum of the GABAergic neuroactive steroids as compared to the Pain/PTSD group [Women: 2.84 vs 2.45] and [Men: 3.6 vs. 2.44] though men displayed a greater difference between the study groups. No significant differences between the groups were found at this time.

Examination of the mean change in NPY from baseline to post five minutes of exercise (when NPY is at its peak) by sex indicated that for the men, the TC group had a greater mean change in NPY than the PTSD group ($m_1=2.35$ ($SD=1.26$) vs $m_2=1.84$ ($SD=.59$) respectively. For the women, the pain/PTSD group had a slightly greater mean change than the TC's ($m_1=2.3$ ($sd=.49$) and $m_2=1.84$ ($sd=.37$) respectively. No significant mean differences were found within or between the two groups at this time.

Additional findings:

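### Hypothesis 2a has no stated estimate or test of the baseline-to-endpoint change in ALLO+PA, so the analysis plan as written cannot answer Aim 2

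*Combined protocol and SAP*

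**What the plan says.** Under Hypotheses or Key Questions, Aim 2 is to "Compare the impact of the exercise training program on plasma levels of the anti-stress neuromodulator" ALLO+PA. Hypothesis 2a then states that, before training, "ALLO +PA will be lower and increase less in response to the maximum load exercise than during the endpoint exercise assessment". It has two parts, the level and the acute rise, and each compares baseline with endpoint.

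The Data Analysis Plan treats Aims 2 and 3 in one short paragraph. At both exercise assessments, "change scores will be computed ALLO+PA and these will be correlated with pain tolerance and pain threshold scores", using Pearson or Spearman coefficients. An exploratory regression then uses ALLO+PA to predict tolerance, threshold and intensity. The Exploratory Aim paragraph adds further correlations and regressions, including correlations of ALLO+PA with pain severity and disability.

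Specific Objectives states that "data from this pilot work will be used to compute effect sizes in support of a future clinical trial". The Power and Sample Size section draws its assumptions from earlier ALLO studies.

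On pain, Aim 3 asks whether ALLO+PA increases "correlate with changes in pain symptoms as measured by the cold pressor test and self-reported pain ratings". Hypothesis 3a expects smaller ALLO+PA rises to be "associated with lesser acute exercise-induced decreases in pain sensitivity and lesser increases in tolerance as measured by the cold pressor test". Hypothesis 3b says endpoint rises "will correlate with increases in pain tolerance/decreases in pain sensitivity when compared to baseline pre-training responses".

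**The concern.** The hypothesis asks about a mean difference between visits, and the stated analysis measures association within visits. A correlation can be strong when training has no effect on ALLO+PA, and absent when training has a large one.

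At stake is the only stated hypothesis under Aim 2, and the ALLO+PA effect size that a later trial would need. The data will exist, so an estimate can still be produced, but its definition would be chosen after the results are visible. The Cardiopulmonary Exercise Test section schedules samples at -15 and 0 minutes, at each workload, and at 5 and 30 minutes after exercise; the pilot also normalised by BMI. Leaving the workload samples aside, there are three pre-exercise choices (-15, 0 or their mean), two post-exercise choices and two normalisation choices: 3 x 2 x 2 = 12 versions of the exercise response.

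**Working it through.** **1. What the stated analysis can show.** For participant i, let B_i and E_i be the exercise-induced ALLO+PA change at baseline and endpoint. The response half of Hypothesis 2a says that mean(E_i - B_i) > 0. The plan reports r(B, pain at baseline) and r(E, pain at endpoint). Replace E_i by E_i + c for everyone. Both correlations are unchanged for any c, and so is the slope of a regression of pain on E at that visit; only its intercept moves. The planned output is therefore the same whether training adds nothing or a large constant. The same holds for resting level. If the change scores were read as between-visit changes, they would still only be correlated with pain; no mean change or interval is reported.

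**2. Whether another analysis fills the gap.** The growth model is introduced for Aim 1. Its listed outcomes are pain intensity, tolerance, threshold, depression and PTSD symptoms. Support for Hypothesis 1 is judged, in part, on the paths from study group to slope. It uses three occasions, with the middle loading freely estimated. Maximum load tests are done only at baseline and at weeks 13-15, so the exercise response has two occasions.

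**3. Whether the data are scheduled.** Yes. Both exercise visits have two pre-exercise samples and a 30-minute sample. The Cold Pressor Test section places a pain test one to five days before each exercise test and another directly after the 30-minute draw. The pilot summarised "mean change in ALLO (normalized by BMI) from baseline to post thirty minutes of exercise by sex", so an interval has been used before, but the analysis section does not adopt it.

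**4. The plan's own sample-size figure.** It gives an effect size of .35, 90% power and two-sided 5%, hence 25 participants, with power .94 at 30. The test and the effect-size metric are not named.
- As a paired standardised difference d_z = 0.35: 88 needed; power 0.39 at 25.
- As Cohen's f with two measures and an assumed within-person correlation of 0.5 (d_z = 0.70): 24 needed; power 0.92 at 25 and 0.96 at 30.
- As Cohen's f with three measures and an assumed correlation of 0.3: 26 needed; power 0.89 at 25 and 0.94 at 30.

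The figure can be neither confirmed nor refuted from the documents, and it is not tied to Hypothesis 2a.

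**5. What a paired contrast would deliver.** Completers: 25 (the stated requirement), or 30 x 0.80 = 24 at the upper dropout figure (30 x 0.82 = 24.6 at the lower). Power comes from the noncentral t with n - 1 degrees of freedom and noncentrality d_z x sqrt(n), two-sided 5%. The CI half-width, in SDs of the paired differences, is t(.975, n - 1)/sqrt(n).

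| Completers | d_z, 80% power | d_z, 90% power | CI half-width |
|---|---|---|---|
| 25 | 0.58 | 0.68 | 2.064/5 = 0.41 |
| 24 | 0.60 | 0.69 | 2.069/4.899 = 0.42 |

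**6. Aim 3.** Aim 3 and Hypotheses 3a and 3b are worded as changes in pain. The analysis sentence attaches change to ALLO+PA and leaves pain as scores, which could be either levels or changes.

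**The case against.** The strongest reply is that the Aim 1 text ends by extending its method to all outcome measures, and that the slope mean there conveys average change. Resting ALLO+PA may even have a third occasion: the Cold Pressor Test section samples it before the pre-exercise pain test and repeats those baseline procedures at mid-point. So the level half of Hypothesis 2a could arguably be covered. This stands only as a possibility. The sentence closes the Aim 1 paragraph, ALLO+PA is absent from its outcome list, and Aims 2 and 3 have their own paragraph. It cannot cover the exercise response.

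A second reply is that this is a proof-of-concept pilot whose main objective is symptom change, with ALLO+PA second, and that the change scores at both visits will already be computed. That limits the consequences and makes the repair easy. It does not supply the missing comparison.

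Stronger readings are tempting and should be resisted:
- A reader might infer that the Aim 3 analysis is wrong. The documents show ambiguity. The pilot related ALLO change to threshold after exercise, which makes a level reading possible; the hypotheses and the paired pain tests make a change reading natural.
- A reader might infer that self-reported pain is dropped apart from the intensity regression. The Exploratory Aim also correlates ALLO+PA with pain severity, though not as a change.
- A reader might infer that the sample size is wrong. Step 4 does not support that.

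**Conclusion.** The point holds for Hypothesis 2a and needs correcting before the data are analysed. No stated analysis estimates or tests the change in ALLO+PA, or in its exercise response, from baseline to endpoint. Followed as written, the plan cannot answer Aim 2 or provide the corresponding effect size. The omission is one of specification, not of data collection.

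The precision figures assume 24 or 25 complete pairs and roughly normal paired differences. They are in SDs of the within-person difference, a quantity the documents do not give, so they cannot be turned into concentration units. They show that the contrast is informative for moderate-to-large effects only, which is a reason to report the interval and not just a p-value.

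The Aim 3 wording is a separate and minor clarification.

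**What to change.** Add to the Aims 2 and 3 paragraph of the Data Analysis Plan paired endpoint-minus-baseline estimates, with 95% CIs and tests, of:

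1. pre-exercise ALLO+PA; and
2. the exercise-induced change, defined as the 30-minute post-exercise value minus the pre-exercise value, which is the pilot interval.

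Name one as primary for Hypothesis 2a. State in advance how the -15 and 0 minute samples are used (for example, their mean) and whether values are normalised by BMI.

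As a separate clarification, for Hypothesis 3a define the pain variable as the score after the exercise test minus the score before it. For Hypothesis 3b, state which change from the baseline visit is meant. One option is the endpoint post-minus-pre change less the baseline post-minus-pre change, but other readings are possible and the choice is the sponsor's.

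The cost is wording and one or two extra tests; naming a primary contrast limits the added multiplicity. No new visit, sample or measure is needed. Participants without an endpoint exercise test do not contribute to the paired estimates, so the number of complete pairs should be reported.
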